### **4.2. Safety Analysis Set**

The Safety Analysis Set is defined as all patients who received at least 1 dose of study rFIXFc. All analyses and summaries of safety, demographics, and baseline characteristics will be based on the Safety Analysis Set, unless otherwise specified in this SAP.

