Statistical Methods:	In general, all statistical analyses will be descriptive in nature. No formal comparison is planned and no hypothesis will be formally tested. Continuous variables will be summarized and presented by the number of observations, mean, median, standard deviation, minimum, and maximum. Categorical variables will be summarized by the number and percentage in each category. Subjects with at least 1 dose of rFIXFc (study drug and/or commercially available rFIXFc) will be included in the Safety Analysis Set. Subjects with at least 1 dose of rFIXFc

CONFIDENTIAL

study drug will be included in the Full Analysis Set (FAS). Subjects with at least 1 dose of rFIXFc study drug and who meet the eligibility criteria (with screening FIX activity and inhibitor test results confirmed by the central laboratory) will be included in the Supporting Analysis Set. Efficacy analyses will be based on the FAS. Safety analyses will be based on the Safety Analysis Set, with some analyses based on the Supporting Analysis Set, as appropriate. Subjects developing a confirmed positive inhibitor test after exposure to rFIXFc study drug will have their efficacy and safety data included up to the time of the last negative inhibitor test; efficacy and safety data collected after the time of the last negative inhibitor test will be summarized separately. Summary statistics will be presented for safety and efficacy endpoints. The proportion of subjects developing inhibitors will be presented with a 95% confidence interval. For efficacy purposes, the number of bleeding episodes will be annualized. The summary statistics of bleeding episodes per person-year and subject's response to treatment will be presented separately for episodic and prophylaxis treatment. Other statistical analyses may be conducted for exploratory purposes.

Interim Analysis:

No interim analyses are planned for this study.

Sample Size Determination:

Because the size of the hemophilia population is limited, the sample size is based on clinical rather than statistical considerations. Taking into account the CHMP Guideline [[EMA \(EMA/CHMP/BPWP/144552/2009\) 2011](#)] and in an effort to enroll a sufficient number of subjects to assess the efficacy and safety of rFIXFc in this population of primarily very young children, approximately 30 subjects will be enrolled to achieve at least 20 subjects with no less than 50 EDs by the completion of the study.

Study Stopping Rules:

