16.5.1. Analysis Population

The Safety Analysis Set is defined as all subjects who receive at least 1 dose of rFIXFc, including study drug and/or commercially available rFIXFc. The primary safety analyses will be based on the Safety Analysis Set including the data collected on or after the time of the first injection of rFIXFc (study drug and/or commercially available rFIXFc).

The Supporting Analysis Set is defined as all subjects who receive at least 1 dose of rFIXFc study drug and meet the eligibility criteria (with screening FIX activity and inhibitor test results confirmed by the central laboratory). Selected safety analyses may be based on the Supporting Analysis Set including the data collected on or after the time of the first injection of rFIXFc study drug.

CONFIDENTIAL

The information contained herein may not be used, disclosed, or published without the written consent of Bioverativ
Therapeutics Inc

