16.5.2. Methods of Analysis

16.5.2.1. Occurrence of Inhibitor Development

The analysis of inhibitor development will be based on the Safety Analysis Set, as defined in Section 16.5.1.

The proportion of subjects who develop an inhibitor during the study will be determined along with the exact (Clopper-Pearson) 2-sided, 95% confidence interval (CI). The main analysis will include all subjects who have received at least 1 dose of rFIXFc (study drug and/or commercially available rFIXFc). Further analyses will be presented for subjects who reach certain ED milestones, to be specified in the statistical analysis plan. For this latter analysis, both the numerator and denominator will include subjects who develop an inhibitor, even if they have not reached the specified ED milestone. One ED is defined as a 24-hour period in which a subject receives 1 or more doses of rFIXFc, with the time of the first injection of rFIXFc defined as the start of the ED.

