### **5.1.1.2. Categorical Variables**

Categorical variables (e.g., adverse event) will be summarized using counts and percentages. All percentages will be rounded and presented to one decimal place, unless otherwise specified in the Statistical Programming Specifications for the study. The denominator for calculating percentages will depend on the variable to be summarized. For example, the denominator for calculating percentage of patients with any adverse event will be the Safety Analysis Set, which is number of patients dosed with rFIXFc.

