### 6.1. Disposition of Patients

Patient disposition will be presented by treatment regimen as described in Section 5.1.1.

This table will present the number and percentage of patients in the Safety Analysis Set and the All-Enrolled Analysis Set. Percentages will be based on the total number of patients who were enrolled in the study, or who received at least 1 dose of rFIXFc.

In addition, the number and percentage of patients in the Full Analysis Set (FAS) and in the FAS with an efficacy period, as well as those in the Surgery Subgroup, the Inhibitor Subgroups, and the ITI Subgroup, will be provided. The number and percentage of patients who completed/ discontinued the study, including the primary reason for those who discontinued, will be tabulated. Percentages will be based on the number of patients in the All-Enrolled Analysis Set.

Patient disposition, including the date of the last visit and the reason for early termination or early withdrawal for patients who did not complete the study, will be provided in a data listing.

The number and percentage of patients enrolled will be summarized by country and site, for the All-Enrolled Analysis Set.

The number of patients attending each key study visit will be summarized by key study visit overall for the Safety Analysis Set, including visits in the main study. If the ITI Subgroup consists of at least 5 patients, this summary will also be performed for the ITI Subgroup, including only visits in the ITI period.

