#### **9.4.3.2. Primary Analysis**

The primary analysis of overall incidence of positive inhibitor formation will be based on all patients in the Safety Analysis Set. Any patient who develops an inhibitor following the initial rFIXFc administration will be included in the numerator. All patients who have received at least 1 dose of rFIXFc will be included in the denominator. An exact 95% confidence interval for the proportion of patients with a positive inhibitor will be calculated using the Clopper-Pearson method for a binomial proportion. PROC FREQ in SAS version 9.4 or higher will be used to produce this confidence interval.

The incidence of positive inhibitor formation will be summarized separately for the types of inhibitor specified in Section 5.2.4, namely:

- Patients with high-titer inhibitors
- Patients with low-titer inhibitors that meet the clinically meaningful criteria
- Patients with low-titer inhibitors that do not meet the clinically meaningful criteria

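### SAP 4.2 and 5.4.5 narrow the Safety Analysis Set and the safety period to study-supplied rFIXFc, contrary to the protocol, and SAP Section 10 does not declare the change

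*SAP*

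**What the plan says.** The protocol is consistent on the population. The synopsis says: "Subjects with at least 1 dose of rFIXFc (study drug and/or commercially available rFIXFc) will be included in the Safety Analysis Set". Section 16.5.1 repeats it: "The Safety Analysis Set is defined as all subjects who receive at least 1 dose of rFIXFc, including study drug and/or commercially available rFIXFc". The same section bases the primary safety analyses on "data collected on or after the time of the first injection of rFIXFc (study drug and/or commercially available rFIXFc"). For the primary endpoint, Section 16.5.2.1 says: "The main analysis will include all subjects who have received at least 1 dose of rFIXFc (study drug and/or commercially available rFIXFc"). Section 7.1 introduces a separate term for the study-labeled supply precisely to set it apart from commercial product.

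SAP 4.2 is narrower: "The Safety Analysis Set is defined as all patients who received at least 1 dose of study rFIXFc". SAP 5.4.5 starts the overall safety period at the first dose of study medication, yet also says when that period ends for patients who fail screening.

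Elsewhere the SAP leaves out the qualifier. SAP 9.4.3.2 bases the primary analysis on the Safety Analysis Set and then says: "All patients who have received at least 1 dose of rFIXFc will be included in the denominator". SAP 5.1.1.2 describes the set as "the Safety Analysis Set, which is number of patients dosed with rFIXFc". SAP 6.1 bases disposition percentages on "patients who were enrolled in the study, or who received at least 1 dose of rFIXFc".

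SAP Section 10 lists three major differences from the protocol: the Full Analysis Set, the dropped Supporting Analysis Set and the health outcomes questionnaire.

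**The concern.** The Safety Analysis Set carries the primary endpoint, so a change to its membership rule is a change to the primary analysis population. It should be declared with at least as much care as a change of questionnaire.

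Two groups are affected:

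- **Patients given only commercial rFIXFc.** Protocol 7.3.1 and 9.1.2 foresee them: bleeds before eligibility may be treated with commercial product, and a subject who needs more than 3 such injections becomes a screen failure. The protocol counts these patients in the main inhibitor analysis; SAP 4.2 does not.
- **Enrolled patients with up to 3 earlier commercial doses.** They are in the set under either definition. However, their adverse events after consent and the first commercial dose, but before the first study dose, fall outside the period in SAP 5.4.5. Protocol 7.1 requires medical observation for the first administration of either supply because of allergic risk, so this is not an empty interval for safety.

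**Working it through.** The documents give no figure to reproduce. The check is a comparison of definitions, followed by an illustration of scale.

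**1. Set membership and data window**

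| Item | Protocol | SAP |
|---|---|---|
| Safety Analysis Set | either supply (synopsis, 16.5.1) | study supply (4.2) |
| Start of safety data | first injection of either (16.5.1) | first study dose (5.4.5) |
| Main inhibitor analysis | either supply (16.5.2.1) | Safety Analysis Set, then a denominator with the supply unstated (9.4.3.2) |
| Declared as a change | – | no (Section 10) |

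**2. Safety Analysis Set against Full Analysis Set.** SAP 4.3 defines the latter as enrolled patients with a study dose. Protocol 9.1.3 has enrollment recorded before study drug is dispensed. The enrollment condition therefore removes almost nobody who meets SAP 4.2, and the two sets practically coincide. Under the protocol they differ by the commercial-only patients.

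**3. Screen-failure clause.** A screen failure has not been enrolled and so should not have received study drug. Patients who fail central testing after study dosing are already enrolled and are withdrawn (Protocol 8.3 and 11). A safety period for a dosed screen failure therefore fits a patient given commercial product, and SAP 4.2 excludes that patient.

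**4. Treatment emergence.** The lead definition in SAP 9.3.1 runs from the first injection of rFIXFc, with no supply named. Its partial-date rule refers to the first dose of study drug. An event between the first commercial and the first study dose is treatment-emergent by the lead definition and outside the safety period by 5.4.5.

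**5. Scale for the primary proportion.** Inputs:

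- n = 30 study-drug patients, taken from the planned enrollment of about 30 (SAP 3.3).
- k = 1 to 3 commercial-only patients without an inhibitor, which is assumed because the documents give no count.
- x = 0, 1 or 2 inhibitor cases among the study-drug patients, also assumed.

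The SAP proportion is x/n and the protocol proportion is x/(n + k). Exact Clopper-Pearson 95% limits are the 0.025 quantile of Beta(x, N − x + 1) and the 0.975 quantile of Beta(x + 1, N − x), where N is the denominator used. The lower limit is 0 when x = 0.

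| x | N = 30 (SAP 4.2) | N = 31 (k = 1) | N = 33 (k = 3) |
|---|---|---|---|
| 0 | 0% (0 to 11.57) | 0% (0 to 11.22) | 0% (0 to 10.58) |
| 1 | 3.33% (0.08 to 17.22) | 3.23% (0.08 to 16.70) | 3.03% (0.08 to 15.76) |
| 2 | 6.67% (0.82 to 22.07) | 6.45% (0.79 to 21.42) | 6.06% (0.74 to 20.23) |

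Shifts in the estimate:

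- x = 1: 3.33 − 3.23 = 0.10 to 3.33 − 3.03 = 0.30 points.
- x = 2: 6.67 − 6.45 = 0.22 to 6.67 − 6.06 = 0.61 points.
- x = 0: only the upper limit moves, by 11.57 − 11.22 = 0.35 to 11.57 − 10.58 = 0.99 points.

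With k = 0 there is no shift from this source.

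**The case against.** The best defense is that the SAP is settled. SAP 9.4.3 and the opening of 9.4.3.2 tie the primary analysis to the Safety Analysis Set, and 4.2 defines that set. The SAP also drops the qualifier elsewhere as shorthand: 4.3 defines the Full Analysis Set by study rFIXFc, and Section 10 describes the same set without the qualifier. This largely stands. A reader might infer that the primary population is undefined. The documents do not go that far: there is a definition, and it is narrower than the protocol's. The unqualified denominator and the screen-failure clause blur it but do not replace it.

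The defense also says the effect is negligible and does not flatter the product. That stands for the proportion. Leaving out patients without an inhibitor raises the estimate slightly, and the shifts are small beside intervals that reach from near 0 to about 17% or 22%. A confirmed inhibitor in a commercial-only patient is unlikely to be recorded. It needs two central samples 2 to 4 weeks apart (SAP 5.2.4), and a screen failure's safety period ends when the failure is confirmed.

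A reader might infer that adverse events would be lost. They would not. Protocol 15.3.1 records them from consent and SAP 9.3 lists all of them; what is uncertain is which events enter the summaries.

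A reader might also see the same fault in exposure-day counting. SAP 6.6.1.1 already gives a rule, counting from the first on-study injection. Passages that mention exposure days without saying where counting starts do not contradict it.

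Finally, Protocol 10.2.6.1 ties its Inhibitor Subgroup to study drug. That governs subgroup handling and does not alter the main-analysis population in 16.5.2.1.

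**Conclusion.** The point holds as an undeclared narrowing of the Safety Analysis Set and the safety period relative to the protocol, with wording inside the SAP that fits it poorly. It does not show material bias in the inhibitor rate. Under the assumed counts the proportion moves by about 0.1 to 0.6 points with 1 or 2 cases, and commercial-only patients may not exist at all.

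It would be too absolute to say that only those patients can matter. The numerator in SAP 9.4.3.2 runs from the initial rFIXFc administration, so a positive sample taken after commercial but before study dosing in an enrolled patient could in principle be treated differently under the two rules.

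The firmer gain from correcting the text is a single rule for adverse events between the first commercial and the first study dose. The size of that effect cannot be computed, because the documents give no number of patients with earlier commercial doses.

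**What to change.** Before database lock, restore the protocol's wording covering both supplies in SAP 4.2 and start the safety period in 5.4.5 at the first injection of either. Use the same terms in the treatment-emergent rule in 9.3.1, including its partial-date clause, and in the denominator sentence of 9.4.3.2.

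If the narrower set is intended, declare it in Section 10 and also report the inhibitor proportion on the protocol-defined set.

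Either way, state how many patients received only commercial rFIXFc and what data exist for them.

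The cost is a few sentences and minor programming, with no new data collection. One limit remains: data on commercial-only screen failures may be sparse. Protocol 10.2.3.2 asks for eCRF entry of commercial dosing for subjects who enrolled, Protocol 15.3.1 keeps adverse events before consent out of the eCRF, and a screen failure may have no confirmatory inhibitor sample.

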### **4.3. Full Analysis Set**

The Full Analysis Set (FAS) is defined as all enrolled patients who receive at least 1 dose of study rFIXFc. All analyses and summaries of efficacy and exploratory endpoints will be based on the FAS, unless otherwise specified in this SAP.

	Statistical Analysis Plan	Final v1.0
---	----------------------------------	-------------------

## 5. DEFINITIONS AND DATA HANDLING

Study 998HB303 is being conducted under the sponsorship of Bioverativ Therapeutics Inc. Data management is being performed under contract with IQVIA in collaboration with Bioverativ. Statistical analysis will be performed by Bioverativ’s Biostatistics Department and/or a designated contract research organization (CRO), using SAS® version 9.4 or higher and, where appropriate, additional validated software. This SAP is based on Version 3 of the approved study protocol dated 06 August 2018 and details the analyses to be performed and summaries to be produced for the final analyses for the Clinical Study Report (CSR).

### 5.1. General Principles

In general, the following approaches will be used in analysis/summary of baseline/demography, safety, efficacy and exploratory endpoint data, unless otherwise specified in this SAP.

No statistical hypothesis testing is planned. However, 95% confidence intervals (CIs) when determined for a binomial proportion will use the Clopper-Pearson method.

#### 5.1.1. Data Presentation

In general, presentations of background/demography and safety data will include an overall/total column and those for efficacy and health outcome data will not. Any exceptions to this are specified in the relevant section.

There is only 1 treatment arm in the study. However, unless otherwise stated, all analyses and background/demography tables will be presented for the following treatment groups, as defined in Section 3.1.2:

- Patients who were ever on an episodic regimen
- Patients who were ever on a prophylactic regimen
- Patients who were ever on an ITI regimen

For longitudinal data, the safety or efficacy periods included for these groups is the time spent on that regimen within that period. These periods are defined in Section 5.3 and 5.4.

Selected tables will also be presented by patients’ inhibitor development status, if there are at least 5 patients in the positive inhibitor subgroup (defined as in Section 5.2.4).

#### 5.1.1.1. Continuous Variables

Continuous variables (e.g., age) will be summarized using the following standard summary statistics: number of patients (n), mean, standard deviation (SD), median, minimum value (min), and maximum value (max). In addition, if specified in the analysis table shells for this study, the 25th and 75th percentiles will also be presented. Summary statistics, excluding minimum and maximum, will be presented to one decimal place beyond that with which the study data were collected. For example, for data collected to no decimal place (e.g., 20 EDs), the mean and median will be presented to 1 decimal place and the SD to 2 decimal places. Minimum and maximum will be displayed as reported in the source data. If the measurements are transformed,

	Statistical Analysis Plan	Final v1.0
---	----------------------------------	-------------------

then the mean, median, SD, minimum, maximum of the transformed measurements will be presented with the appropriate precision.

Unless impractical within a table of analysis results, statistics will be aligned by the decimal place in the summary tables (even if not displayed in this manner in the table shells).

### **5.1.1.2. Categorical Variables**

Categorical variables (e.g., adverse event) will be summarized using counts and percentages. All percentages will be rounded and presented to one decimal place, unless otherwise specified in the Statistical Programming Specifications for the study. The denominator for calculating percentages will depend on the variable to be summarized. For example, the denominator for calculating percentage of patients with any adverse event will be the Safety Analysis Set, which is number of patients dosed with rFIXFc.

### **5.1.1.3. Event Time Variables**

The only such variable being analyzed in this study is the time to inhibitor (see Section 5.2.4 for complete definition). The cumulative incidence of these inhibitors over time (EDs) will be estimated using the Kaplan-Meier method and presented graphically.

### **5.1.2. Pooling Sites for Analysis**

All sites will be pooled and reported together for analysis.

## **5.2. Study Definitions**

### **5.2.1. Study Days**

Study day for an event will be calculated from the first dose of study drug as (date of event – first dose date + 1) if the date of event is on or after the first dose date, or (date of event – first dose date) if the date of event is before the first dose date. That is, Study Day 1 is the first day of treatment with study drug. Study Day -1 is the day immediately preceding Study Day 1. There is no Study Day 0 in this study. Study days will be included in the data listings where indicated on the listing shells. “NA” for “not applicable” will be used to indicate that a patient did not receive the respective study drug.

### **5.2.2. Baseline**

Unless specified otherwise, for the purpose of analyses involving change from baseline during treatment with rFIXFc, baseline is defined as the last non-missing measurement (that can be used for data analysis i.e. was not taken during a surgical/rehabilitation period) taken prior to the first dose of study medication rFIXFc.

If a patient requires rescreening during the study, then baseline characteristics for the summary table will be taken from the first screening visit.

### **5.2.3. Visit Windows**

	Statistical Analysis Plan	Final v1.0
---	----------------------------------	-------------------

### **Screening Visit**

Screening assessments to determine subject eligibility for the study will be collected within 8 weeks after the first Screening Visit (i.e., the first visit for any activity other than informed consent, which can occur prior to the subject’s birth). If more than 8 weeks elapse and screening activities have not been completed, the inhibitor and factor IX activity blood draws must be repeated. Other screening assessments that have not yet been completed must be completed within an additional 8 weeks.

### **Baseline Incremental Recovery Visit**

Baseline IR Visit assessments are performed as soon as practicable once all eligibility criteria have been met and the patient has been enrolled. The Baseline IR Visit activities may be completed on the same day as Screening, or they may be completed as a part of a separate visit or at an unscheduled visit. Samples for IR calculations are taken when the patient is in a non-bleeding state, after at least a 72 hour washout.

